7. VARIABLES AND METHODS

7.1 Efficacy Parameters

7.1.1 *Clinical Efficacy Parameters*

7.1.1.1 *Pruritus*

Pruritus in both ears will be assessed by the investigator at all visits. For consistency, the same individual should perform all the assessments at all visits, if possible. Pruritus will be assessed as:

- Severe (3) if pruritus is marked or intense
- Moderate (2) if pruritus is definitely present
- Mild (1) if pruritus is slight
- Absent (0) if there is complete absence of pruritus

At Visits 2, 3 and 4, pruritus will be considered resolved if the level is 0. Pruritus will be considered improved if the level is lower than the previous pruritus assessment.

7.1.1.2 *Otalgia*

Otalgia in both ears will be assessed at all visits. The investigator will ask the patient to assess his or her level of otalgia on the day of the visit. If the patient has taken analgesic medication, he or she will be asked to assess the level of otalgia before taking the analgesic. For consistency, the assessment of otalgia should always be performed before the ear is examined. Assessments will be on the scale described in Blanch 2000.¹⁵ Otalgia will be assessed as:

- Severe (3) if it interferes with activities of daily living;
- Moderate (2) if it causes discomfort but does not interfere with activities of daily living;
- Mild (1) if there is awareness of pain but not much discomfort; or
- Absent (0) if there is total absence of pain.

At Visits 2, 3 and 4, otalgia will be considered resolved if the level is 0. Otalgia will be considered improved if the level is lower than the previous otalgia assessment.

7.1.1.3 *Ear fullness*

Ear fullness (aural fullness or ear pressure) in both ears will be assessed by the investigator at all visits. For consistency, the same individual should perform all the assessments at all visits, if possible. Ear fullness will be assessed as:

- Severe (3) if ear fullness, is marked or intense
- Moderate (2) if ear fullness is definitely present
- Mild (1) if ear fullness is slight
- Absent (0) if there is complete absence of ear fullness

At Visits 2, 3 and 4, ear fullness will be considered resolved if the level is 0. Ear fullness will be considered improved if the level is lower than the previous ear fullness assessment.

7.1.1.4 Otorrhea

Otorrhea in both ears will be assessed by the investigator at all visits. For consistency, the same individual should perform all the assessments at all visits, if possible. Otorrhea will be assessed as:

- Severe (3): copious discharge that prevents visualization of the tympanic membrane unless the fluid is suctioned
- Moderate (2): the anterior sulcus is full, but the tympanic membrane is still clearly visible
- Mild (1): little fluid accumulating in the anterior tympanomeatal sulcus but the tympanic membrane is still visible
- Absent (0) absence of fluid

At Visits 2, 3 and 4, otorrhea will be considered resolved if the level is 0. Otorrhea will be considered improved if the level is lower than the previous otorrhea assessment.

7.1.1.5 Overall Clinical Outcome

Overall Clinical Outcome is based on the TSSS, which is calculated by the sum of pruritus score + otalgia score + ear fullness score + otorrhea score. Patients will be allocated to one of the following categories for Overall Clinical Outcome:

1. Clinical Cure: TSSS is 0, as defined in Sections 7.1.1.1, 7.1.1.2, 7.1.1.3 and 7.1.1.3.
2. Clinical Improvement: TSSS is different than 0 but lower than the previous visit, as defined in Sections 7.1.1.1, 7.1.1.2, 7.1.1.3 and 7.1.1.47.1.1.3.
3. Clinical Failure: TSSS does not meet the definitions of Clinical Cure or Clinical Improvement, as defined in Sections 7.1.1.1, 7.1.1.2, 7.1.1.3 and 7.1.1.4.
4. Not changed: TSSS is different than 0 but unchanged compared to the previous visit.
5. Indeterminate: Discontinued (for reasons other than Clinical Failure) or lost to follow-up.

Patients who take rescue medication (as defined in section 6.7.2) will be considered Clinical Failures.

7.1.2 Mycological Efficacy Parameters

7.1.2.1 Mycological Outcome

Samples of ear discharge will be taken at V1, and in addition at visits V2, V3 and V4, when discharge is present. The otorrhea/debris sample will be taken prior to the debridement of the affected ear. A central laboratory will provide exudate sampling kits with standardized instructions for sample preparation (as defined in the Laboratory manual).

The otorrhea/debris sample will be sent to the Central Laboratory for processing. The central laboratory will be blinded to the treatment assignment of the patient from whom the sample was taken.

The central laboratory will use standardized microbiological laboratory procedures to identify fungal and bacterial species.

Susceptibility testing on fungal isolates will be performed according the Clinical and Laboratory Standard Institute methods for clotrimazole and comparator drugs to which the fungal isolates are susceptible.

For any patient with a culture positive for fungi at Visit 1, mycological outcome at Visit 2 will be classified as:

- Eradication if the culture does not show growth of any fungal pathogen;
- Presumed Eradication if there is no material to culture and the Overall Clinical Outcome is Clinical Cure;
- Persistence if any fungal pathogen cultured at Visit 1 is still present;
- Presumed Persistence: if there is no material to culture and the Overall Clinical Outcome is not Clinical Cure;
- Superinfection if a fungal pathogen not present at Visit 1 is now present (presence of a nonpathogenic organism will not be considered Superinfection); or
- Indeterminate if none of the above definitions are met and the mycological outcome cannot be determined.

For any patient with a culture positive for fungi at Visit 1, mycological outcome at Visit 3 will be classified as:

- Eradication if the culture does not show growth of any fungal pathogen;
- Presumed Eradication if there is no material to culture and the Overall Clinical Outcome is Clinical Cure;
- Persistence if any fungal pathogen cultured at Visit 1 is still present;
- Presumed Persistence: if there is no material to culture and the Overall Clinical Outcome is not Clinical Cure;
- Recurrence: if there is reappearance of the fungal pathogen eradicated or presumably eradicated at Visit 2;
- Superinfection if a new fungal pathogen is isolated while the initial pathogen is also present (presence of a nonpathogenic organism will not be considered Superinfection);
- Reinfection: if there is isolation of a new fungal pathogen different from the one eradicated or presumably eradicated at Visit 2; or
- Indeterminate if none of the above definitions are met and the mycological outcome cannot be determined.

For any patient with a culture positive for fungi at Visit 1, mycological outcome at Visit 4 will be classified as:

- Eradication if the culture does not show growth of any fungal pathogen;
- Presumed Eradication if there is no material to culture and the Overall Clinical Outcome is Clinical Cure;
- Persistence if any fungal pathogen cultured at Visit 1 is still present;
- Presumed Persistence: if there is no material to culture and the Overall Clinical Outcome is not Clinical Cure;
- Recurrence: if there is reappearance of the fungal pathogen eradicated or presumably eradicated at Visit 2 and/or 3;
- Superinfection if a new fungal pathogen is isolated while the initial pathogen is also present (presence of a nonpathogenic organism will not be considered Superinfection);
- Reinfestation: if there is isolation of a new fungal pathogen different from the one eradicated or presumably eradicated at Visit 2 and/or 3: or
- Indeterminate if none of the above definitions are met and the mycological outcome cannot be determined.

Mycological outcome will be determined for each patient for Visit 2, Visit 3 and for Visit 4 after mycological culture results are made available to the Sponsor or designee.

Mycological cure is defined as eradication (culture does not show growth of any fungal pathogen) or presumed eradication (there is no material to culture and overall clinical outcome is clinical cure).

7.1.3 Therapeutic response

The therapeutic response is a combined assessment of the Overall Clinical Outcome plus the Mycological Outcome. The following categories are defined:

1. Therapeutic cure: TSSS (pruritus + otalgia + ear fullness + otorrhea) = 0 and mycological outcome eradication or presumed eradication.
2. Therapeutic failure:
 - Positive fungal culture, OR
 - TSSS > 0 regardless of mycological outcome.

7.1.4 Primary Efficacy Endpoint

Based on the definitions in Section 7.1.1.5, 7.1.2 and 7.1.3, the primary efficacy endpoint will be the proportion of patients with Therapeutic cure at Test of Cure (Visit 4) in the mycological intended-to-treat (MITT) population.

7.1.5 Secondary Efficacy Endpoints

Based on the definitions in Sections 7.1.1, 7.1.2 and 7.1.3, the secondary efficacy endpoints will be:

- Overall clinical cure at Visits 2, 3 and 4.
- Mycological cure at Visits 2, 3 and 4.
- Therapeutic cure at Visit 2 and 3.
- Changes in TSSS at Visits 2, 3 and 4.
- Changes in individual signs and symptoms at Visits 2, 3 and 4.

In the case of bilateral otomycosis the non-selected ear will also be treated and assessed for its clinical evolution.

7.2 Safety Parameters

Safety will be assessed by AEs and physical examination. In addition, a urine pregnancy test for females of childbearing potential will be performed at Visit 1.

Adverse events will be recorded throughout the study and at early termination, and will be coded using the Medical Dictionary for Regulatory Activities (MedDRA).

The investigator is responsible for the detection and documentation of AEs regardless of treatment group or suspected causal relationship to the investigational product. For all AEs, the investigator must pursue and obtain information adequate to determine the outcome of the AE and to assess whether the AE meets the criteria for classification as an SAE requiring immediate notification to the Sponsor or its designated representative.

7.2.1 Adverse Events

7.2.1.1 Definitions

An AE is any untoward medical event that occurs in a patient or subject who has received an investigational product, whether or not considered drug related. An AE can therefore be any unfavorable and unintended sign (including abnormal laboratory finding), symptom, or disease temporally associated with the use of an investigational product, whether or not related to the study product.

An illness present at entry to the study is considered a pre-existing condition and will not be considered an AE. However, if a pre-existing condition worsens during the study, this may be considered an AE. Pre-existing conditions will be documented in the EDC. If pre-existing signs and signs/symptoms of otomycosis (pruritus, otalgia, ear fullness and otorrhea) worsen during the study, this will be considered a treatment failure instead of an AE. All AEs, including intercurrent illnesses, that occur during the study (i.e., between Informed Consent Form (ICF) signature and Visit 4) must be reported and documented as described below.

7.2.1.2 *Timing*

Adverse events will be assessed from the time the subject provides informed consent.

Serious adverse events should be collected for up to 30 days after the last dose of study medication.

At study termination, subjects with ongoing AEs/SAEs should be followed up by the Investigator for as long as medically indicated. The Sponsor retains the right to request additional information for any subject with ongoing AEs/SAEs at the end of the study, if judged necessary.

7.2.1.3 *Recording Adverse Events*

Volunteered, observed, and elicited AEs will be recorded. This includes AEs the patient reports spontaneously, those the Investigator observes, and those elicited in response to questions from the study staff. Patients will be asked open-ended questions, such as "How have you been feeling since your last visit?", at each study visit. If a patient reports any pain or illness during or after administration of the eardrops (i.e. itching), the pain or illness experienced by the patient should be recorded as an AE.

All AEs that occur during the study must be recorded in the Adverse Events page of the EDC. All Adverse Event EDC entries should contain a brief description of the event, date and time of onset, duration, intensity, treatment required, relationship to study medication, action taken with regard to study medication, outcome, and whether the event is classified as serious.

7.2.1.4 *Assessment of Adverse Event*

Each AE will be assessed by the Investigator with regard to the following categories.

7.2.1.4.1 *Serious Adverse Event*

International Conference on Harmonization (ICH) Guidelines and federal regulations define a SAE as any untoward medical occurrence that at any dose results in any of the following outcomes:

- death;
- life-threatening. This means that the patient is at risk of death at the time of the event; it does not mean that the event hypothetically might have caused death if it were more severe;
- requires or prolongs patient hospitalization (any hospitalization except observational admissions of less than 24 hours);
- results in persistent or significant disability or incapacity; or
- congenital anomaly or birth defect.
- important medical events that may not result in death, be life threatening, or require hospitalization may be considered as an SAE when, based upon appropriate medical judgment, they may jeopardize the subject and may require medical or surgical intervention to prevent one of the outcomes listed in this definition.

If an event meets any of the above definitions, regardless of the severity or relationship of the event to the study product, the event must be reported to the Sponsor or Sponsor's designee as described in Section 7.2.1.3.

Adverse events reported from clinical studies associated with hospitalization or prolongation of hospitalization are considered serious. This category also includes transfer within the hospital to an acute/intensive care unit (e.g., from a standard of care unit to an acute/intensive care unit).

Hospitalization does not include the following:

- Rehabilitation facilities, hospice facilities or respite care (e.g. caregiver relief)
- Nursing homes or skilled nursing facilities
- Emergency room visits
- Same day surgeries (as outpatient/same day/ambulatory procedures)
- <24 hour admissions for observation or evaluation

Hospitalization or prolongation of hospitalization in the absence of a precipitating, clinical AE is not in itself an SAE. Examples include:

- Admission for treatment of a preexisting condition that did not worsen
- Protocol-specified admission (e.g. for a procedure required by the study protocol)
- Hospitalizations for cosmetic elective surgery, social, and/or convenience admissions
- Pre-planned treatments or surgical procedures should be noted in the baseline documentation for the individual subject.
- Diagnostic and therapeutic procedures, such as surgery, should not be reported as AEs; however, the medical condition for which the procedure was performed should be reported if it occurs during the reporting period and meets the definition of an AE. For example, an acute appendicitis that begins during the AE reporting period should be reported as an AE, and the resulting appendectomy should be recorded as treatment of the AE.

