The dosing regimen for the clotrimazole solution approved in the UK (CANESTEN) is 2-3 drops of solution in the ear two or three times a day at least 2 weeks (the minimum amount of clotrimazole is 0.74 mg/administration and 1.48 mg/day, and the maximum amount of clotrimazole is 1.11 mg /administration and 3.33 mg/day).

Clotrimazole was also shown to be safe and effective in treating otomycosis with perforated tympanic membrane when administered as a Clotrimazole 1% solution in PEG 400 for up to 3 weeks in 40 patients either delivered using an impregnated Q-tip or an ear wick. Patients were reported to have tolerated both treatments very well. Two patients (11%) had some burning in the first two days of treatment. Itching was gradually relieved over the first week in all patients. The tympanic membrane looked normal in all patients following treatment and perforations closure was noted in 4 out of 40 patients (Abou-halawa et al., 2012)¹⁴.

Overall, clotrimazole is reported to be safe and effective regardless of the route of administration with no ototoxic effects reported in any of the clinical studies.

SALVAT has completed EBEROTIII/11IA01 where safety and efficacy of Eberconazole 1% otic solution was compared with Clotrimazole 1% otic solution (CANESTEN solution) in patients with otomycosis. The study was a multicenter, randomized, parallel-group, double blind phase III non-inferiority study comparing the clinical efficacy and safety of Eberconazole 1% otic solution

compared with Clotrimazole 1% otic solution for the treatment of otomycosis as assessed by mycological evaluation, otoscopic examinations (pruritus, otorrhea and aural fullness), otalgia, and AEs. A total of 190 patients aged 18 years or older were included and treated with either Clotrimazole 1% otic solution (n=95) or Eberconazole 1% otic solution (n=95) 5 drops twice daily for 14 days.

The main efficacy variable consisted of a combination of clinical and mycological evaluation (complete response). The majority of the patients had a complete response to the treatment, with similar percentages in both groups (83.5% in the clotrimazole group and 81.8% in the eberconazole group; $p=0.0789$; intent-to-treat (ITT) population). These results showed that both drugs are effective in the treatment of otomycosis, although the non-inferiority of eberconazole with respect to clotrimazole was not demonstrated.

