5. STUDY POPULATION

5.1 Inclusion Criteria

1. At least 18 years of age at Visit 1 (Day 1, Screening/Baseline).
2. Clinical diagnosis of fungal otitis externa (otomycosis) in one or both ears, where topical treatment is indicated.
3. Presence of at least two of the following symptoms at baseline: of pruritus, otalgia and ear fullness.
4. Presence of debris and/or drainage clinically consistent with fungal infection, i.e. white or black appearance consistent with *Aspergillus* spp. or *Candida* spp.
5. Otorrhea/debris sample for bacterial and mycological cultures.
6. Provide written informed consent.
7. Willing and able to follow all instructions and attend all study visits.
8. Females who are not pregnant, not lactating and are not planning a pregnancy during the study. All females of childbearing potential (those who are not premenstrual, not postmenopausal or not surgically sterile) will be able to participate only if they have a negative urine pregnancy test at baseline (prior to randomization), and if they agree to use adequate birth control methods to prevent pregnancy throughout the study.

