8.2 Observations by Visit

8.2.1 Visit 1

Patients who may be eligible to participate in the study will be offered the opportunity to participate. The study will be explained to them and questions about the study will be answered. Patients who elect to participate will sign the Informed Consent Form (or have it signed by their legally authorized representative), before any study procedures may be performed. The IWRS will assign a patient number, which will be used to identify the patient during screening and, if applicable, throughout the duration of the study. Patients who do not meet the inclusion and exclusion criteria will be registered as screen failures through the IWRS. Patients who have provided consent and met the inclusion and exclusion criteria will be enrolled and randomized through the IWRS.

Medical history, concurrent symptoms and conditions, and concomitant medications will be recorded, and a physical examination (as described in Section 7.2.3) will be performed. Female patients of childbearing potential will have a urine pregnancy test.

Pruritus, otalgia, ear fullness and otorrhea will be evaluated as described in Sections 7.1.1.1, 7.1.1.2, 7.1.1.3 and 7.1.1.4. A sample of ear discharge will be obtained for bacterial and mycological cultures as described in Section 7.1.2 prior to the debridement of the ear.

The patient will be given a medication kit containing a 14-day supply of study medication. The blind will be maintained as described in Section 6.4. A member of the study staff will instruct the patient on how to open the vials and administer study medication, and will supervise the patient during administration of first dose. Day 1 will be the day when the first dose is administered (important if due to unforeseen circumstances the first dose is administered the day after the baseline visit).

Patients will be instructed to refrain from swimming during the study treatment period and preferably until the final study visit is completed. Patients will also be advised to use a shower cap or neoprene head band when bathing.

A visit calendar will be provided to the patient.

If any AEs occur during Visit 1, they will be recorded in the Adverse Events page of the EDC.

8.2.2 Visit 2

Visit 2 will take place on Day 8-10. AEs and concomitant medications will be recorded and vital signs will be assessed.

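### For pruritus or otalgia present at entry, Protocol 7.2.1.1 and 7.2.1.3 give opposite recording rules for worsening after the drops, so non-serious local reactions may be recorded unevenly and missed in the TEAE tables

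*Protocol*

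**What the plan says.** Protocol 7.2.1.1 (Definitions) treats an illness present at entry as a pre-existing condition whose worsening may be an AE, then makes an exception for the disease under study. The sentence opens "If pre-existing signs and signs/symptoms of otomycosis (pruritus, otalgia, ear fullness and otorrhea" and, once the bracket closes, ends "worsen during the study, this will be considered a treatment failure instead of an AE". SAP 2.3.2.1 repeats the exception.

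Protocol 7.2.1.3 (Recording Adverse Events) covers what a patient reports around dosing. Its rule for such complaints reads: "during or after administration of the eardrops (i.e. itching), the pain or illness experienced by the patient should be recorded as an AE". The same section lists what each AE entry must hold, including "relationship to study medication, action taken with regard to study medication, outcome, and whether the event is classified as serious".

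Protocol 7.2 adds a general duty: "The investigator is responsible for the detection and documentation of AEs regardless of treatment group or suspected causal relationship to the investigational product".

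Inclusion criterion 3 (Protocol 5.1) requires: "Presence of at least two of the following symptoms at baseline: of pruritus, otalgia and ear fullness".

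Protocol 10.1.11 and SAP 3.5.1 define TEAEs to include events that began before the first dose and then became more severe.

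**The concern.** Itching is pruritus and ear pain is otalgia. When a patient who entered with one of these reports that it is worse after the drops, 7.2.1.1 keeps the event off the AE page and 7.2.1.3 puts it on. An investigator can follow either section in good faith.

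Local tolerability is an obvious safety question for an ear drop, and safety here rests mainly on AEs. If sites divide on the rule, the same event counts at one and not at another. The TEAE, related-AE and AE-discontinuation tables then partly reflect site habit. The TEAE definition cannot repair this, because it sorts events already entered as AEs.

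**Working it through.** The plan states no figure on this point, so the check is a comparison of the texts plus two small enumerations.

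**1. The two rules side by side**

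| Event | Protocol 7.2.1.1 | Protocol 7.2.1.3 |
|---|---|---|
| Itching or ear pain present at entry, worse after the drops | Not an AE | AE |
| Itching or ear pain new after the drops | Exception does not apply | AE |
| Another local reaction, such as burning | Exception does not apply | AE |
| Ear fullness or otorrhea present at entry, worse | Not an AE | Not named |

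Only the first row is a direct contradiction.

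**2. Precedence.** 7.2.1.1 closes by pointing forward to the reporting sections, so the two are linked. The link does not say that 7.2.1.3 overrides the exception. 7.2.1.3 does not exempt symptoms present at entry and sets no time limit on what counts as after a dose. With two doses a day for 14 days (Protocol 6.2), most worsening on treatment is after some dose.

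**3. Reach.** Two or more of pruritus (P), otalgia (O) and fullness (F) gives four combinations: P+O, P+F, O+F and P+O+F. All four contain P or O. In scores of 0 to 3:
- exactly two of the three non-zero: 3 pairs × 3 × 3 = 27
- all three non-zero: 3 × 3 × 3 = 27
- times four otorrhea levels: (27 + 27) × 4 = 216 eligible profiles
- with both P and O non-zero: 3 × 3 × 4 × 4 = 144

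All 216 have pruritus or otalgia. This shows in whom the conflict can arise, not how often it does.

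**4. What the efficacy tables recover.** SAP 3.4.2 and 3.4.2.2 give severity by visit, mean change per symptom and a change class. Their limits are:
- *Change class.* Mild to severe and mild to mild both fall under Not improved.
- *Severity counts and means.* Take two patients in one arm, one going from mild (1) to severe (3) and one from severe (3) to mild (1). The visit still shows one mild and one severe, and the mean change is (+2 − 2)/2 = 0.
- *Overall outcome.* This uses the summed TSSS. Scores for pruritus, otalgia, fullness and otorrhea of 2, 1, 2, 2 sum to 7; 1, 3, 1, 0 sum to 5. That is Clinical Improvement although otalgia rose from mild to severe. Of 20,736 possible Visit 1 to Visit 2 score pairs in which pre-existing pruritus or otalgia rises, 6,133 still class as Clinical Improvement: 6,133/20,736 = 29.6%. This is a count of patterns, not a probability.
- *Coverage.* Efficacy analyses use the evaluable ear only (SAP 3.4). Unscheduled data stay out of the summary tables (Protocol 10.1.3). Otalgia is rated for the day of the visit (SAP 2.3.1.1.2).
- *Content.* A score carries no relationship assessment; an AE entry does.

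**The case against.** The strongest defence is that the sections have different subjects: 7.2.1.1 concerns progression of the disease, already scored as efficacy, and 7.2.1.3 concerns reactions to the drops. Keeping disease symptoms out of AE counts is a deliberate convention. This is a sensible split and probably the intended one, but it is not written. It also asks the investigator to judge cause before deciding whether to record, whereas Protocol 7.2 requires documentation whatever the suspected cause.

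That the SAP carries only the 7.2.1.1 rule proves little, since sites record under the protocol. It does mean that the SAP offers no help in resolving the conflict.

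Several safeguards stand:
- An occurrence that meets a serious criterion must be reported whatever its severity or relationship (Protocol 7.2.1.4.1).
- Staff supervise the first dose (Protocol 6.2), and AEs during Visit 1 are recorded (Protocol 8.2.1).
- Patients are asked open questions at each visit (Protocol 7.2.1.3). These can bring an event to light, but they do not tell the site which rule then applies.
- Severity and mean change are tabulated for each symptom, so the otalgia rise in the TSSS example would enter the severe count for that visit.
- Rescue use is tabulated by arm (SAP 3.3.5), and all data are listed.
- In bilateral disease the second ear is also assessed (SAP 2.3.1.5), although the efficacy analyses do not use it.

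Together these narrow the gap to non-serious worsening and its causality assessment. They do not close it.

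**Conclusion.** The concern holds as a conflict between two stated recording rules for pruritus and otalgia present at entry. Non-serious worsening after instillation may be recorded differently across sites and be missing from the TEAE and related-AE tables. Every eligible patient could meet the conflict. The number of events affected is unknown and may be zero, because the documents give no rate and all sites may follow 7.2.1.3.

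A reader might infer more than the documents support:
- *That the primary endpoint is altered by the words treatment failure.* It is not. Protocol 7.1.4 builds the endpoint from the clinical, mycological and therapeutic definitions, not from 7.2.1.1.
- *That serious local events could go unreported.* Protocol 7.2.1.4.1 covers them.
- *That all local reactions are excluded.* New symptoms and other reactions remain AEs, and no direct contradiction is shown for ear fullness or otorrhea.
- *That the TEAE definition contradicts 7.2.1.1.* It does not; it applies to whatever has been recorded.
- *That the comparison is biased towards one arm.* Nothing shows this; the demonstrated risk is inconsistency and under-recording.

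The conclusion rests on the wording alone. Site training or eCRF instructions outside these documents may already settle the matter.

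**What to change.** 1. Reconcile Protocol 7.2.1.1, Protocol 7.2.1.3 and SAP 2.3.2.1 with a stated precedence. Worsening of a pre-existing symptom that the patient reports in connection with instillation, within a window that the sponsor defines, goes on the AE page whatever the suspected cause, and relationship is assessed afterwards. Other worsening stays an efficacy outcome. Without a window the ambiguity returns, given twice-daily dosing.
2. Add to the SAP one descriptive Safety-population table by arm: patients whose score for any of the four signs or symptoms rose above Visit 1 in any treated ear at a scheduled visit, and how many have a matching AE entry. State the reference score for an ear treated only from Visit 2. Label the table as mixing disease worsening with local reaction, since it cannot separate them. Keep unscheduled scores in the listings, in line with Protocol 10.1.3.
3. If enrolment has ended, do item 2 and query unmatched rises with the sites before database lock, while still blinded. SAP 3.3.2 already plans a blinded review at that stage.

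Cost: item 1 needs a protocol amendment with IRB/IEC approval (Protocol 11.4). Items 2 and 3 use scores already collected in both ears at every visit, so they need programming and query time only. AE counts may rise somewhat, and some of the added events will be disease-related. The SAP also covers CLEAR-1, so a SAP change would reach both trials.
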